#### **Remote consent**

In situations where in-person consent is not possible or acceptable to the woman and econsent is not possible (i.e. no access to a computer or the internet) remote documented consent will be undertaken. The PIL and ICF will be sent by post to the woman. The informed consent discussions will proceed as detailed in sections 5.1.1 by telephone).

The recruiting centre/hub staff will initial the boxes on the ICF during the discussion with the woman, sign and date the ICF, and then send a copy of the completed ICF to the woman for her records.

After explicit consent has been provided by the participant the original ICF will be placed in the ISF a copy will be scanned and sent securely to the ABA-feed Trial Office. A record of details of the informed consent discussions will be sent to the recruiting centre to be recorded in the participant's hand-held or electronic maternity notes. This will include date of discussion, the name of the trial, summary of discussion, version number of the PIL given to participant and version number of ICF signed and date consent received.

# 5.2. Consent for future research

Consent to longer-term follow-up will take two formats.

First, we will ask women whether they would be willing for us to obtain their routinely collected data on primary care consultations and hospital admissions for themselves and their babies, when their babies reach 12 months of age.

Second, we will ask mothers whether they are willing to be approached after study completion to find out how they and their baby are getting on.

# 5.3. Consent for qualitative interviews

Women, IFHs and key informants (e.g. infant feeding leads, peer support manager, midwifery staff, health visitors and children's centre managers – see 15.2) will be invited for interview or focus group by post or email, with the PIL and consent form attached, or by text message with a web link to the PIL and consent form.

If a researcher is able to meet the participant in person then written informed consent will be used. The participant will be given the opportunity to ask questions before the signing and dating of the latest version of the ICF for the qualitative study. The research fellow will then sign and date the interview/focus group ICF.

If in-person consent is not possible, the participants will have been sent/emailed both the PIL and consent form and the informed consent discussion and consent process will be recorded using an encrypted audio-recorder. The audio-file will be saved in a password protected university folder at the earliest possible opportunity and deleted from the audio-recorder. The research fellow will initial the boxes on the ICF in discussion with the participant, sign and date the ICF and then send a copy to the participant. The consent process will be audio-recorded in a separate recording, which will be kept separate from the interview audio file.

The interview audio file will be sent securely to a specialist transcription company and will be handled in accordance with the Data Protection Act 2018. The interviewees must consent to this on the ICF for the qualitative study.

# 6. IDENTIFICATION, SCREENING, ENROLMENT AND RANDOMISATION

#### 6.1. Identification

The methods for approaching women have been selected to reduce inequalities in access and uptake and ensure a broad reach.

Several recruitment methods will be used, not only to maximise participation in the trial, but also to make it resilient to any future COVID related restrictions or moves to a more pragmatic approach from the health care providers. Approach (i) (see below) was used successfully in the feasibility trial and we had ethical approval for the approach outlined in section (ii). Two additional approach pathways (iii) and (iv) cover any COVID restrictions or service preferences.

A PIL will be provided to facilitate whichever process is used. An audio version for women with low literacy will be available on the study website. Investigators or delegate(s) will ensure that they adequately explain the aim, trial intervention, anticipated benefits and potential hazards (unlikely to be any due to the low-risk nature of the trial) of taking part in the trial to the participant. They will also stress that participation is voluntary and that the participant is free to refuse to take part and may withdraw from the trial at any time.

(i) As in the ABA feasibility study, community midwives and other direct care staff in the recruiting centres will be asked to hand out a summary PIL to women who are pregnant with their first child at an antenatal appointment (e.g. at their 16- or 25-week antenatal appointment), or the summary PIL will be emailed/sent/made available electronically. At a subsequent antenatal appointment (e.g. at 28 weeks), a researcher/staff member will be available in the clinic so that women who have been given information by a direct care staff member will be available to offer further information about the study, including a full PIL, and give the women an opportunity to ask any further questions, providing women have indicated that they would be interested in participating in the study. The women will have the option of signing up to the study there and then, or having time to think about it and/or discuss with others before contacting the researcher to arrange a time and place to enrol. Women will only be able to enrol in the study up until 35+6 weeks gestation to allow sufficient time for intervention participants to meet with their IFH before birth.

(ii) A researcher or CRN research midwife will be available in 20-week ultrasound anomaly scan clinics. Direct clinical care staff will point out the researcher/research midwife so that women can approach them for further information about the study. Nearly all women (99%) attend the 20-week anomaly scan.

(iii) Community midwives or a hospital staff member will invite women who attend their antenatal clinic or 20-week scan to complete an agreement to contact form where they will provide their contact details and give agreement to be contacted by the research team to discuss the study. Members of the health visiting team may invite women to complete an agreement to contact form at their antenatal contact. This agreement will be documented in the maternity record. If an approach or clinical contact is over the phone or using another remote technology, then verbal assent to contact by the research team will be taken. Details will be collected on the woman's name, email and telephone number and passed to the recruiting centre/hub staff undertaking recruitment.

(iv) Other forms of remote invitation will be included: including the use of social media to invite women to take part (e.g. Facebook posts, twitter, advertising the study using the study poster); posters in antenatal and scan clinics and other places frequented by pregnant women (with QR code linking to study website); direct email invitations sent from maternity or health visiting services, with a link to the study website.

# 6.2. Screening and enrolment

In the ABA-feed Trial, members of staff / researchers who are delegated the task on the ABA-feed Trial Delegation Log will confirm eligibility prior to randomisation.

Non-English speaking women will be included conditional to finding suitable arrangements to accommodate language requirements; e.g., we will use IFHs with community language

skills, where they are available. Where no IFH with appropriate language skills is available we will investigate using link workers as interpreters and use of language lines.

If no resource to provide translation and language support is available the women will not be included in the trial.

At recruitment we will inform women that we wish to compare two different ways of supporting new mothers in feeding their new baby. One way will be that women receive information from their community midwife and antenatal classes before birth and from their midwife and other community services after birth. The alternative will also involve a new ABA-feed infant feeding team who will meet the mother before she gives birth and after the baby is born and will contact the mother regularly by telephone and text to answer feeding queries and offer advice and support.

The research team at recruiting centres and hubs will maintain a Participant Screening/Enrolment Log, which will include data on the numbers of women with whom there was a conversation about participating in the trial but were not entered into the trial along with the reasons for non-enrolment. We will not be able to collect information on numbers of women receiving information via social media, posters, and summary information leaflets handed out in clinics by midwives.

Women who meet the eligibility criteria will be considered eligible and subsequently randomised to the trial.

# 6.3. Randomisation

After eligibility has been confirmed and informed consent has been received (as outlined in section 5) and the baseline questionnaire completed, the woman can be randomised into the trial.

Randomisation will be provided by a secure online randomisation system at the Birmingham Clinical Trial Unit (BCTU). Unique login usernames and passwords will be provided to those who wish to use the online system and who have been delegated the role of randomising participants into the study as detailed on the ABA-feed Trial Training Log and ABA-feed Delegation Log. The online randomisation system will be available 24 hours a day, seven days a week, apart from short periods of scheduled maintenance. A back-up telephone toll-free randomisation service ([name]) is available Monday to Friday, 09:00 to 17:00 UK time, except for bank holidays, government guided closures and University of Birmingham closed days.

An Eligibility/Randomisation Form will be provided to investigators and will be used to collate the necessary information prior to randomisation. If any data items are missing, randomisation will be stopped, but can be restarted once the information is available. Only when all eligibility criteria and baseline data items have been provided will a Trial Number be allocated.

The ABA-feed trial is individually randomised. We have inflated the sample size in the intervention group only to account for the effect of potential clustering by feeding helper in the analysis, so randomisation would allocate more women to the intervention arm than control (1606 vs 1124).

Women will be randomised by computer at the level of the individual participant in a 1.43:1 ratio to either ABA-Feed or the control group. A minimisation algorithm will be used within the online randomisation system to ensure balance in the treatment allocation over the following variables:

- site
- woman's age (<25, ≥25)

A 'random element' will be included in the minimisation algorithm, so that each woman has a probability (unspecified here), of being randomised to the opposite treatment that they would have otherwise received. Full details of the randomisation specification will be stored in a confidential document at BCTU.

Following randomisation, a confirmatory e-mail will be sent to the research team at the relevant Hub and the ABA-feed Trial Office.

# 6.4. Allocation concealment

Due to the allocation by computer, allocation is concealed from those responsible for recruiting women into the study.

# 6.5. Blinding

This is an unblinded trial and all trial participants and care providers will be unblinded to allocation. Due to the two interventions under study being so different (usual care for infant feeding versus additional proactive feeding support by IFHs), it is not feasible to have a blinded design. There are different management implications for the participants following their allocated intervention and therefore the research staff need to be aware of the intervention received. There is no substantial risk and the intervention will adhere to the policies and quality standards of the participating local trusts/local authorities/health boards.

BCTU Statisticians will be unblinded to allocation for such purposes as interim analysis and/or data cleaning.

We will keep primary and secondary outcome data separate from process evaluation data for analysis.

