# 3.2. Trial Setting

The trial will be undertaken in approximately 10-15 sites. Each site is an English local authority area (or NHS Health Board in Wales or Scotland), or part of a local authority area with low breastfeeding rates. Sites are selected for usual care that doesn't deliver universal proactive peer support antenatally and postnatally for first time mothers. The sites will be managed from five hubs across the UK (Universities of Birmingham, Bristol, Cardiff, Central Lancashire and Stirling, supporting 2-4 sites per hub). Research Fellows (RF) and Project Officers (PO) will be employed at each of the Hubs to work alongside the Hub Leads. Their role will be to manage local aspects of the trial.

Organisation	Role
BCTU	Oversight, trial management, monitoring, database development,
	statistical analysis and oversight of general conduct
Hubs	Liaison with sites in their geographical regions
	Recruitment remotely
	Recruitment within trusts/health board premises with research
	passports
	Qualitative interviews and other process evaluation components
Recruitment centres: NHS	Recruitment
trusts; health boards and	Identification of pregnancy loss, stillbirth or neonatal death
NHS premises	
Sites	Geographical areas where women live where the ABA-feed
	intervention will be delivered

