#### 8.3.2. Follow-up assessments

All other follow-up assessments will be managed directly from the ABA-feed Trial Office. There will be no subsequent assessments following stillbirth or infant death.

• An automated text message will be sent at 3-days postnatal, with responses by text message, which will be directly linked with the trial database;

- An emailed link to an online questionnaire will be sent at 8-, 16- and 24-weeks to all women willing to complete questionnaires online;
- A paper questionnaire will be sent, with pre-paid addressed return envelope, at 8-, 16- and 24-weeks to all women who elected to complete questionnaire on paper; this will be returned to the ABA-feed Trial Office and entered by a data manager or delegated staff member;
- Telephone follow-up will be undertaken for participants who elected for this form of follow-up (BCTU / Hub).

Hub and recruiting centre staff will collect 8-week feeding records from health visiting records.

	Concention	Describer	Text			14/2 - 1- 24
	Screening	Baseline	day 3	March Oreart	Mark 10	Week 24
	(before	(before	post	Week 8 post	Week 16	post birth
	36/40)	36/40)	birth	birth	post birth	(-14 to
	weeks	gestation	(+ 10	(+ 30 or –	(+ 30 or –	+10 days)
Visit	gestation	weeks	days)	14 days)	14 days)	
Eligibility check	x					
Valid informed consent	x					
Relevant obstetric history taken	x					
Demographic data	x					
Infant feeding plans	x					
Randomisation		x				
Infant feeding status			x	x	x	X
Details of mode of birth				x		
Health & social resource use				x	x	
Infant feeding difficulties				x		
Self-reported formula feeding						
practices				x	x	
EQ-5D-5L		x		x	X	
GAD-7		x		X	X	
MOS social support		x		x	x	
Infant deaths		x	x	X	x	

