At 8-, 16- and 24-weeks post birth a web-link for completion of an online questionnaire with the option to request a paper version will be sent; women who requested paper questionnaires at baseline will be posted a questionnaire by the recruiting centre/ hub or the ABA-feed Trial Office. The ABA-feed Trial Office will transcribe the data from completed paper CRFs to the online database when the CRF is returned to the Trial Office.

Non-responders will be sent a text question about feeding and a reminder to complete the questionnaire. Missing 8-week feeding method will be sought by researchers from routinely collected data, as in the ABA feasibility study.

The database system will include data validations to improve data quality (e.g. to prevent nonsensical dates or numerical values). Changes to the data, on the system, will be made by ABA-feed Trial Office staff and will be documented and attributable where the Trial Office transcribes this data.

On-site monitoring will, for the most part, be triggered by poor recruitment or poor data returns. CRFs may be checked against the source data where on-site monitoring is conducted and must be available for verification.

A bespoke password protected database will be developed to record details of contacts between a woman and the IFH and actions taken (e.g. mode of contact and any advice to seek further help). It will have a function to enable a photo of the woman's family and friends diagram to be securely stored. The family and friends diagram will not include any personal identifiers (woman's first name only). The database will only include the woman's trial number and initials. The record will only be visible to the local IFH team (IFH manager and IFHs in the locality to enable cross cover of support if needed) and the ABA-feed team at BCTU.

Audio recordings of qualitative interviews will be collected on encrypted recorders and sent securely for transcription. Records will be sent securely to the University of Birmingham and stored as password protected documents on secure University of Birmingham Servers.

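### Section 6.5 gives research staff the allocation for a reason that does not cover phoning for, abstracting or cleaning the 8-week feeding status

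*Protocol*

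**What the plan says.** Section 6.5 of the protocol states that participants and care providers know the allocation. For staff it reasons: "There are different management implications for the participants following their allocated intervention", and "therefore the research staff need to be aware of the intervention received". No role or task is excepted. It adds: "BCTU Statisticians will be unblinded to allocation for such purposes as interim analysis and/or data cleaning".

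Other sections show which staff handle the primary outcome:

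- Section 8.2.1: the outcome is self-reported in the 8-week questionnaire or by a later text, and gaps are filled from health visitor records.
- Section 8.3.2: women who chose telephone follow-up are phoned by BCTU or a Hub. For the records route, "Hub and recruiting centre staff will collect 8-week feeding records from health visiting records".
- Section 10.4: "Missing 8-week feeding method will be sought by researchers from routinely collected data".
- Section 10.3, Table 4: the Trial Office transcribes questionnaires returned on paper.
- Section 6.3: after randomisation "a confirmatory e-mail will be sent to the research team at the relevant Hub and the ABA-feed Trial Office".

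The only related safeguard in 6.5 is that outcome data and process evaluation data are kept apart for analysis. Nothing is said about collection or cleaning.

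**The concern.** Women and infant feeding helpers (IFHs) cannot be blinded in this trial. Staff who ask about, look up or clean a yes/no feeding status can be, at least in part. The protocol treats the two situations alike and supports both with an argument about managing participants, which applies only to the first.

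Two routes of bias are left open. One is recording: prompting on the phone, reading an unclear record entry or resolving a query with the arm in view. The other is recovery: searching harder for missing outcomes in one arm. Section 13.4 leaves women with missing outcomes out of the primary analysis and reports that most feasibility non-responders were formula feeding, so unequal recovery changes the observed rates. Neither route depends on women knowing their own arm, and both can be narrowed at little cost.

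**Working it through.** **1. The reason set against the tasks**

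| Task | Who (section) | Does different management after allocation require the arm? |
|---|---|---|
| Delivering support | IFHs, feeding leads (7.1.2) | Yes |
| Passing news of a loss to the feeding team | Trial Office, sites (9.2) | Yes, for intervention women |
| Phoning for 8-week status | BCTU / Hub (8.3.2) | No |
| Abstracting 8-week records | Hub, recruiting centre (8.3.2, 10.4) | No |
| Transcribing paper forms | Trial Office (10.3) | No |
| Cleaning the outcome variable | Statisticians (6.5) | No |
| Comparative DMC tables | Statisticians (6.5, 13.5) | Needs it, for a different reason |

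**2. The plan's own sample size**, which supplies the scale (section 13.1: 44% v 51%, 90% power, two-sided 5%, ICC 0.039, 12 women per IFH, 5% loss)

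- Per group, pooled variance: n = [1.960·√(2·0.475·0.525) + 1.282·√(0.44·0.56 + 0.51·0.49)]² / 0.07² = 1,068 after rounding up. This matches.
- Design effect 1 + 11 × 0.039 = 1.429; 1,068 × 1.429 = 1,526. Total 1,526 + 1,068 = 2,594. This matches.
- 2,594 / 0.95 = 2,730.5, stated as 2,730.
- Effective intervention size 1,526 / 1.429 ≈ 1,068. The standard error of the risk difference under no effect is √[0.44·0.56·(1/1,068 + 1/1,068)] = 0.0215.

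None of these figures changes with the fix.

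**3. Recording bias (illustration)**

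Let s be the share of outcomes obtained or resolved by staff. Let b be the difference between arms in recorded breastfeeding, within that share, caused only by knowing the arm. The false risk difference is d = s × b. Two-sided type I error is Φ(d/0.0215 − 1.96) + Φ(−d/0.0215 − 1.96). The protocol gives neither s nor b, so every value below is an assumption.

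| s | b (points) | d (points) | d as share of 7 points | Type I error |
|---|---|---|---|---|
| 5% | 2 | 0.1 | 1% | 5.0% |
| 10% | 5 | 0.5 | 7% | 5.6% |
| 20% | 5 | 1.0 | 14% | 7.5% |
| 20% | 10 | 2.0 | 29% | 15.4% |

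**4. Unequal recovery (illustration)**

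Take a true rate of 44%. In one arm a fraction u is left unrecovered, of whom a fraction q are breastfeeding; the other arm is complete. The observed rate rises by u(0.44 − q)/(1 − u).

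- u = 2%: 0.02 × 0.04 / 0.98 = 0.1 point at q = 40%; 0.02 × 0.34 / 0.98 = 0.7 point at q = 10%.
- u = 5%: 0.05 × 0.04 / 0.95 = 0.2 point at q = 40%; 0.05 × 0.34 / 0.95 = 1.8 points at q = 10%.

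Under the section 13.4 sensitivity analysis, where missing counts as not breastfeeding, the same arm is instead understated by u × q. For q between 0 and 44% the two analyses err in opposite directions, so together they partly expose this route. They do not expose recording bias.

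**The case against.** The strongest reply is that this is an openly unblinded pragmatic trial in which little of the primary outcome passes through staff discretion. Most women answer online, on paper or by text. Telephone is only for those who chose it, and section 10.1 does not even list it among the follow-up routes. The health visitor entry already exists and is copied. Paper originals are source data, and changes made by the Trial Office are attributable (10.1, 10.4). Women know their arm whatever staff know. All of this stands and limits the size of the problem. It does not supply a reason for phoning, abstracting or cleaning with the arm in view.

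Section 10.4 also leaves cleaning procedures to a Data Management Plan that is not shown. It may add masking, but 6.5 as written points the other way.

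Several stronger readings are tempting, and the documents do not support them:

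- *Every member of staff is told the arm.* The text refers to the research staff without exception, but uses the word all only for participants and care providers. Section 6.3 does not say that the e-mail names the arm.
- *These staff judge whether an admission is related to feeding.* No section assigns that task. Section 9.1 has women report admissions and reasons themselves.
- *Only the delivery team and the DMC statistician need the arm.* Loss notification differs for intervention women (9.2), the BCTU team can see the IFH contact log (10.4), and interviewees are sampled by arm (15.2.2, Appendix 3), with Hubs responsible for "Qualitative interviews and other process evaluation components" (3.2).
- *Hub staff's other roles taint the outcome.* Recruitment precedes a concealed allocation (6.4), and the women's interviews follow the 8-week assessment (15.2.2).
- *The bias has a known direction and no analysis touches it.* Chasing the intervention arm harder could lower its observed rate, and section 13.4 partly probes unequal recovery.

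**Conclusion.** The point holds in a limited form. Section 6.5 justifies staff awareness of allocation by participant management. That does not extend to telephone collection, abstraction, transcription or cleaning of the 8-week feeding status, and the protocol masks none of these.

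The size is unknown because the staff-handled share is not stated. Plausible small values give a shift of 0.1 point (5% share, 2-point difference) to 0.5 points (10% share, 5-point difference), with type I error of 5.0% to 5.6%. Shifts of 1 to 2 points need a 20% share and a difference of 5 to 10 points, and nothing in the protocol shows that either is likely. A reader might infer that the primary result as a whole is compromised by staff unblinding. The documents do not support that: reporting by unblinded women dominates the outcome, and masking staff would not remove it. The change is worth making because it is cheap and closes an unnecessary route, not because a large bias has been shown.

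**What to change.** Amend section 6.5 so that staff who phone for, abstract, transcribe or clean the primary outcome do so with the arm hidden where possible:

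1. Call lists and record-search lists carry the identifiers needed to reach the woman or find her record, but not the arm.
2. Calls use scripted wording for the primary outcome question.
3. The number of contact attempts and the extent of the record search are the same in both arms.
4. Outcome data are cleaned on an extract without arm.

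State in the same section which roles keep the allocation: intervention delivery, birth and loss notification to the feeding team, oversight of the IFH log, process evaluation sampling and interviews, and preparation of DMC tables.

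Reporting how many 8-week outcomes came by each route (questionnaire, text, telephone, records), by arm, would let readers judge the exposed share.

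Cost: some database permission work and a wording change, with existing staff and no change to the sample size. Masking will be partial, since women may reveal their arm on the phone and some Hub staff will already know it.
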